6. STUDY PROCEDURE

To disguise the true purpose of the study, participants will be told that the study aims to investigate daily fluctuations in mood after accounting for lifestyle factors such as diet and sleep. To bolster the cover story, participants will complete mood ratings before and after eating each meal and computerised tasks assessing categorisation of positive versus neutral words at lunchtime during each study day. Participants will also complete a sleep quality questionnaire on each study day to distract from the focus on food intake. Data from mood and sleep measures will not be analysed.

Figure 1 presents the sequence of steps in the study that are described **Table 2**. Occasionally, exceptions to the general rule will be made in order to fit within a participant’s schedule.

[figure not shown]

Figure 1. Participants’ schedule

Table 2. Description of the study procedure

RECRUITMENT	
 ▪ Participants respond to recruitment materials via email/phone ▪ Information sheet sent over email with link to online pre-screening questionnaire (Qualtrics) ▪ Eligible participants are invited to a screening session in person to formally check that they meet the eligibility criteria
--------------------	--

SCREENING SESSION Informed consent	
 ○ Ensure participants have read information sheet and explain the study in more details ○ Measure height and weight ○ Confirm eligibility ○ Participants sign the consent form and keep a copy ○ Organise the study with the participants: 
 ○ Record contact information and preferred communication (text, call or email) ○ Organise individual schedule ○ Explain FitBit use and physical activity restriction ○ Discuss allowed food / drink ○ Participants complete the baseline questionnaire: 
 ○ Demographic questions ○ Portion size appropriateness ○ Stroop task
RANDOMISATION	
 ▪ Participants will be randomly assigned to receive the larger portion sizes at the first experimental session and the smaller portion sizes at the second experimental session or vice versa. ▪ A randomisation sequence will be created using Random Allocation Software [35] with a 1:1 allocation stratified by highest educational qualification (Group 1: low ≤ A level, 18-25 years; Group 2: low ≤ A level, 26+ years, Group 3: ≥ degree, 18-25 years, Group 4: ≥ degree, 26+ years). ▪ The allocations will be placed inside envelopes for each group; the envelopes will be sequentially opened each time a participant from one group consent to take part in the study. ▪ Participants' two experimental sessions should take place on the same day of the week
STUDY DAY 1	
 ▪ Remind allowed food / drink, physical activity restriction and install the FitBit ▪ Sleep, mood, and hunger ratings ▪ Breakfast 30 minute session between 7 am and 10:30 am ▪ Snack box 
 ○ Provide the snack box after breakfast ▪ Lunch 30 minute session (between 12pm and 2pm) ▪ Dinner 30 minute session (between 5pm and 7pm – at least 4 hours after lunch) ▪ Organise the following steps: 
 ○ Remind the date of the next session (washout)
WASHOUT SESSION	
 ▪ Participants return FitBit device and snack box ▪ Check if any additional foods/drinks consumed ▪ Remind participants about date of next session (Study Day 2)

STUDY DAY 2	
 ▪ Remind allowed food / drink, physical activity restriction and install the FitBit ▪ Sleep, mood, and hunger ratings ▪ Breakfast 30 minute session between 7 am and 10:30 am ▪ Snack box 
 ○ Provide the snack box after breakfast ▪ Lunch 30 minute session (between 12pm and 2pm) ▪ Dinner 30 minute session (between 5pm and 7pm – at least 4 hours after lunch) ▪ Organise the following steps: 
 ○ Remind the date of the next session (final session)
FINAL SESSION	
 ▪ Participants return FitBit device and snack box ▪ Check if any additional foods/drinks consumed ▪ Battery of measures 
 ○ Barratt Impulsiveness Scale ○ Satiety responsiveness ○ Plate clearing tendencies ○ Perceived food insecurity ○ Resource availability in childhood ○ Food choice motives ○ Compensatory health beliefs ▪ Study experience questionnaire ▪ Debriefing: explain the purpose of the study, the cover story and provide opportunity to ask questions ▪ Financial compensation (£70)

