(*Level 6: degree apprenticeship; degree with honours – for example bachelor of the arts (BA) honours, bachelor of science (BSc) honours; graduate certificate; graduate diploma; level 6 award; level 6 certificate; level 6 diploma; level 6 NVQ; ordinary degree without honours*)
 - Master's degree or equivalent
(*Level 7: integrated master's degree, for example master of engineering (Meng); level 7 award; level 7 certificate; level 7 diploma; level 7 NVQ; master's degree, for example master of arts (MA), master of science (MSc); postgraduate certificate; postgraduate certificate in education (PGCE); postgraduate diploma*)
 - Doctorate or equivalent
(*Level 8: doctorate, for example doctor of philosophy (PhD or Dphil); level 8 award; level 8 certificate; level 8 diploma*)

We will also aim to stratify recruitment by age (50% 18–25 years; 50% 26+ years), with equal proportions of each age group in each education group (lower, higher).

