7.4. Primary analyses

7.4.1. Confirmatory analyses

To be consistent with previous studies we ran investigating the effect of SEP on intended energy consumption (e.g [45]), the primary measure of SEP used in our primary analysis will be highest educational qualification (binary – lower vs higher).

A mixed ANOVA will be used to test the effect of portion size (categorical: larger, smaller; within-subject), SEP (categorical: lower (\leq A level), higher ($>$ A level), between-subjects), the interaction portion size*SEP on daily energy intake. If the interaction between portion size*SEP is significant the analysis will be stratified by SEP (\leq A level, $>$ A level) and two repeated-measures t-tests will be used to examine the effect of portion size (larger vs smaller) on daily energy intake in the two groups of participants separately. We will not correct for multiple comparisons as we specified a priori hypotheses.

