7.4.2. Sensitivity analyses

Sensitivity analyses will be conducted to examine whether the pattern of results from the main analyses differ after 1/ excluding participants guessing the aims of the study, 2/ excluding outliers on main outcome variables (identified as those with a value $>$ 3SD from condition mean) and influential cases (identified as those with a Cook's distance $>$ 1, indicating a multivariate outlier [37], 3/

substituting SEP measure (highest educational qualification, \leq A level, $>$ A level) with alternative measures of SEP (level of education – composite score, subjective socioeconomic status (1-10), and household income).

The main analyses will also be repeated controlling for any non-SEP based demographic variables (e.g. BMI, age) that significantly differ between the higher vs. lower SEP groups in order to examine if results remain consistent. To examine whether the order that portions are presented impacts the findings, the main analyses will be repeated with an additional 2-level between-subjects factor (portion size order: smaller, larger vs larger, smaller). Finally, the main analyses will be repeated with dishware size as an additional 2-level within-subjects factor (dishware size: smaller vs larger).

We will report whether sensitivity analyses result in deviations from the pattern of significance to the main analyses (i.e., any significant differences between conditions becoming not significant, and vice versa).

Note if $>30\%$ participants guess the study aim we will include aim guessing as a between-subjects factor in ANOVA rather than use listwise removal.

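### Age group is a stratification factor but is absent from the primary ANOVA, and the significance-triggered age adjustment is a weak safeguard for the portion size × SEP interaction

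*Combined protocol and SAP*

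**What the plan says.** - **Randomisation (section 6, Table 2).** The order of the two portion sizes is allocated 1:1 within four groups formed by education and age: "Group 1: low ≤ A level, 18-25 years; Group 2: low ≤ A level, 26+ years", plus the same two age bands for the higher group.
- **Recruitment (section 4.1).** "We will also aim to stratify recruitment by age", half aged 18–25 and half 26 or over, "with equal proportions of each age group in each education group". This is an aim, not a fixed quota.
- **Primary model (section 7.4.1).** "A mixed ANOVA will be used to test the effect of portion size", SEP (binary education) and "the interaction portion size*SEP on daily energy intake". Age is not a term.
- **Sensitivity analysis (section 7.4.2).** The main analyses are repeated "controlling for any non-SEP based demographic variables (e.g. BMI, age) that significantly differ between the higher vs. lower SEP groups". Section 7.1 describes the baseline tests, t-tests or Mann-Whitney for continuous variables and chi-square for categorical ones. The plan does not say whether the adjustment would include an age × portion size term.
- **Sample size (section 7.6).** The minimum is 46, for f=0.175, 85% power and a within-subject correlation of 0.7. The same number is said to serve the portion size × SEP interaction. Recruitment may extend to 60.

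**The concern.** The plan treats age as important enough to shape both recruitment and randomisation, then leaves it out of the confirmatory model without giving a reason. Two consequences are possible.

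First, any difference in the PSE between age groups stays in the error term and costs some power.

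Second, SEP is not randomised, so the portion size × SEP interaction is an observational comparison of two groups of about 23. Only success in recruitment keeps age and education apart. The recruitment routes in section 4.1 (university lists, and if needed letterbox drops focused on deprived areas) could bring in different age mixes, and section 7.6 acknowledges uncertain recruitment. If the split drifts and age moderates the PSE, part of an age difference would be read as an SEP difference. The planned protection applies only when a baseline test is significant, and at this sample size such a test often misses a real imbalance.

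**Working it through.** **Inputs.** From section 7.6: f=0.175, ρ=0.7, N=46 (possibly 60). From section 7: two-sided α=0.05. A 50/50 education split gives 23 per SEP group. Two quantities are assumptions, because the documents give neither: d, the difference in PSE between age bands in within-band SDs of the PSE; and q, the difference between SEP groups in the share aged 26+.

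**1. The plan's figure.** For m=2 conditions, λ = f²·N·m/(1−ρ) = 0.030625 × 46 × 2 / 0.3 = 9.39 on 1 and 44 df. Power is 85.0%. At N=45 it is 84.2%, so 46 is the smallest adequate N and the stated figure reproduces. The interaction at the same f has the same λ and the same power.

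**2. Scale of the effects.** With outcome SD σ, the SD of a participant's PSE is σ√(2(1−0.7)) = 0.775σ. So f=0.175 means an average PSE of 2×0.175/0.775 = 0.45 SD, and for the interaction a between-group PSE difference of 4×0.175/0.775 = 0.90 SD.

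**3. Cost of leaving age out.** An omitted balanced two-level factor multiplies the error variance of the PSE by 1+d²/4, which divides λ by the same factor. This takes the plan's ρ as describing variation within an age band.

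| d | 1+d²/4 | Power without age, N=46 | N=60 |
|---|---|---|---|
| 0 | 1 | 85.0% | 93.1% |
| 0.3 | 1.0225 | 84.2% | 92.6% |
| 0.5 | 1.0625 | 82.8% | 91.6% |

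With age group and age group × portion size included, residual df fall from 44 to 43 at N=46 and power remains 85.0% (93.1% at N=60).

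**4. Bias in the interaction.** With two conditions, the interaction test compares individual PSEs between SEP groups. If the share aged 26+ differs by q, the expected bias is q×d. At N=46 and d=0.5:

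| q | Bias (SD of PSE) | Share of the 0.90 SD planned effect | Type I error |
|---|---|---|---|
| 0 | 0 | 0% | not inflated |
| 0.1 | 0.05 | 5.5% | 5.3% |
| 0.2 | 0.10 | 11% | 6.2% |
| 0.3 | 0.15 | 17% | 7.7% |

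At q=0 the unadjusted test is slightly conservative: simulated type I error is 4.2% at d=0.5 (24 per group, exact age balance).

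**5. The trigger.** A true age difference of 0.5 SD between SEP groups is significant in a t-test with 23 per group only 38% of the time, and one of 0.3 SD only 17%. On age band, a split of 14/9 against 9/14 is a gap of 5/23, or 22 points. Its uncorrected chi-square is 46×(14×14−9×9)²/23⁴ = 2.17, p=0.14. The adjustment would not be made, while the bias at d=0.5 would be 0.22×0.5 = 0.11 SD.

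**6. Which age term matters.** An age main effect cancels from each participant's within-person difference. Only an age × portion size term changes the interaction test.

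**The case against.** The strongest reply is that the plan already deals with age by design and by analysis. Equal age proportions in each education group make age band orthogonal to SEP, and section 7.4.2 names age as a variable to control. Age is also not among the candidate explanations for a larger PSE in section 1, so the documents give no reason to expect d to be large.

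Much of this stands. With the planned split there is no bias, and the power cost at d of 0.3 to 0.5 is about 1 to 2 points. What does not stand is relying on the conditional adjustment: step 5 shows that a 22-point gap can pass the test.

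Some stronger readings are tempting, and the documents do not support them:

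- *Randomisation within age strata protects the SEP comparison, and the model discards that protection.* What is randomised is portion order. Balance of age across SEP comes from recruitment alone.
- *Omitting age by itself contaminates the SEP interaction.* That needs both a missed recruitment split and a PSE that varies with age.
- *Age confounds the portion-size main effect.* Every participant receives both sizes.
- *Age might matter as much as the plan assumes SEP does.* At d=0.90, power at N=46 would be 78.0%, but nothing in the documents supports that value for age.

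**Conclusion.** This is a minor but real gap, and closing it costs almost nothing. The primary model omits a factor used in both recruitment and randomisation, and the fallback depends on a test with little power at about 23 per group. At N=46 the loss is from 85.0% to about 84.2% (d=0.3) or 82.8% (d=0.5), for the main effect and equally for the interaction at f=0.175. The interaction carries a bias of q×d only if the age split drifts: zero as planned, 0.10 SD for a 20-point gap with d=0.5. Both d and q are assumptions. If the PSE does not vary with age, neither consequence arises. If the plan's ρ=0.7 already contains age-related variation, the power comparison becomes a gain from adjusting rather than a loss from omitting. The stated sample size is correct on its own inputs.

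**What to change.** In section 7.4.1, pre-specify age group (18–25, 26+) and age group × portion size as terms in the primary mixed ANOVA. At minimum, make the age-adjusted analysis in section 7.4.2 unconditional and state that it includes the age × portion size term.

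The cost is a line or two of text and 1 residual degree of freedom; age is already collected. If the split drifts, the adjusted interaction also pays a variance factor of 1/(1−q²), about 1.04 at a 20-point gap. The change should be made before any data are analysed.

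The amended text should not claim too much. A two-level term does not remove all age-related variation, because the 26+ band is open-ended. Nor do these terms reproduce the four strata: there is no age × education term, and the definitions do not agree. Table 2 labels the higher strata as degree or above, while sections 4.1, 7.2.2 and 7.4.1 start the higher group just above A level, so participants with a CertHE or DipHE have no stated stratum. Those passages need to be reconciled first.

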7. STATISTICAL ANALYSIS

All statistical analyses will be performed using SPSS (Version 26.0). The level of significance will be set at $p < 0.05$ for primary analyses and $p < 0.01$ for secondary analyses to account for multiple testing.

7.1. Participant's characteristics

A table will present the baseline characteristics. The table will include gender, age, ethnic group, employment status, highest educational qualification, years in higher education, household income, subjective socioeconomic status and BMI for all the participants and for lower and higher education groups. Continuous variables will be summarised using means and standard deviations. Categorical variables will be summarised using counts and percentages. We will test for baseline differences between SEP groups (higher vs lower) on demographic variables using t-tests (or if data does not meet parametric assumptions – i.e. not normally distributed – Wilcoxon Mann-Whitney tests will be used) and chi-square tests.

7.2. Variables description

7.2.1. Primary outcome

Daily energy intake i.e., energy (kcal) from breakfast, lunch and dinner (main and dessert) in the lab, from the snack box and any self-reported additional foods consumed, summed to provide daily energy intake.

Secondary outcomes

Hunger and fullness. Each participant will have 12 measures of hunger and fullness: [breakfast, lunch, dinner] x [pre meal, post meal] x [larger portion size, smaller portion size]. Daily hunger and fullness ratings across time will be summarised by calculating the area under the curve (AUC) using the trapezoid function [36].

Physical activity will be operationalised as ‘active minutes’ per day which are logged for activities with a metabolic equivalent (MET) of ≥ 3 .

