3. EXPERIMENTAL DESIGN

Participants will be randomised into a cross-over design with two study days corresponding to two conditions: larger portion size condition or smaller portion size condition. Each study day will last one day and be separated by a minimum 1-week and maximum 6-week washout period. The two study days will be scheduled for the same day each week. On both days, participants will be served all meals *ad libitum* in the lab (including breakfast and second helpings) and will be provided with snacks to consume outside of the lab – but only the size of the initial portion of the main meal provided for lunch and dinner will be manipulated. Energy intake from all meals and snacks will be recorded.

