5. METHODS

5.1. Test meals

The portion-manipulated test meals will consist of a pasta-based dish for lunch (3 cheese pasta), and a dish served with rice for dinner (chilli con carne), see Table 1 for more information about the dishes. The portion sizes are informed by pilot studies, including pilot studies conducted to assess the norm range, with portions in the larger portion size condition from the mid-higher end of the range, and portion sizes in the smaller portion size condition from the lower end of the norm range (see **Appendix A**).

Table 1. Portion sizes for each portion-manipulated dish in g and kcal

	Larger portion size (100%)			Smaller portion size (67%)		
	g	kcal	£	g	kcal	£
Lunch						
3 cheese pasta	563	816	2.46	375	544	1.64
Dinner						
Chili con carne & rice	437	509	0.90	291	339	0.60
Dinner including cheese and vegetables on the side (totals)	557	737	1.24	411	568	0.94

On each study day, all participants will receive the same *ad libitum* breakfast in the lab (initial serving providing 1437 kcal) and the same snack box for consumption away from the lab throughout the day (providing 906 kcal). At lunch, participants will have the opportunity to serve themselves more of the main dish. At dinner, participants will be served their main dish with a side of vegetables and they will also have the opportunity to request seconds of the main dish. After their dinner a dessert buffet with three options will be provided (providing 1528 kcal). Chilled water (500mL) will be served with each in-lab meal. The complete study menu can be found in SEP_portion_size MENU_UPDATED_TL.xlsx.

Participants will be requested 1/ not to consume any additional food apart from the items provided as part of the study, and 2/ drink only tea, coffee, and no calorie drinks (water) as they usually would.

Note for each self-service breakfast meal we will also vary the size of the dishware (smaller vs larger), the results of which will be reported in detail elsewhere. Given evidence to date (e.g. [47,48]), we expect this to have no impact on energy intake at breakfast, and this will be tested in analyses (see analysis plan). Manipulation of dishware size (smaller followed by larger dishware size

vs larger followed by smaller dishware size) will be fully counterbalanced with the order of portion size presentation (smaller followed by larger portions vs larger followed by smaller portions).

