5.2.4. Hunger and fullness

Participants will rate their current level of hunger and fullness on visual analog scales ranging from 0 to 100 before and after eating each meal in the lab.

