7.5.2. Hunger and fullness

To investigate whether portion size reduction is associated with increased hunger/decreased fullness repeated-measures t-tests will be used to test the effect of portion size (categorical: larger, smaller; within-subject), on AUC for hunger and fullness.

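### The hunger and fullness AUC starts before breakfast although portion size is first manipulated at lunch; starting it at the pre-lunch rating would usually give a more precise portion-size test

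*Combined protocol and SAP*

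**What the plan says.** Section 5.2.4 has hunger and fullness rated "before and after eating each meal in the lab". Section 7.2.1, under secondary outcomes, counts 12 measures per participant, which is six per study day: before and after breakfast, lunch and dinner. It then reduces each day to one number: "Daily hunger and fullness ratings across time will be summarised by calculating the area under the curve (AUC) using the trapezoid function". Section 7.5.2 gives the purpose, "To investigate whether portion size reduction is associated with increased hunger/decreased fullness", and compares the AUC between the two portion conditions with repeated-measures t-tests. Section 7 sets p < 0.01 for secondary analyses.

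On the exposure, section 3 says "only the size of the initial portion of the main meal provided for lunch and dinner will be manipulated". Section 5.1 adds that on each study day "all participants will receive the same *ad libitum* breakfast in the lab", and that the snack box is also the same. Breakfast dishware size does change between days, fully counterbalanced with portion order.

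Nothing starts the AUC at lunch, adjusts for the pre-lunch ratings or adds a lunch-onwards sensitivity analysis. The time axis of the AUC is not stated.

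**The concern.** Three of the six daily ratings (pre-breakfast, post-breakfast, pre-lunch) are taken before the two conditions differ in portion size. The area they span cannot respond to portion size. It does carry day-to-day variation in appetite, any morning snacking, and any effect of breakfast dishware. All of this enters the paired difference that section 7.5.2 tests.

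What is at stake is precision. Section 7.5.2 is the plan's only test of whether smaller portions leave participants hungrier or less full. It is judged at the stricter 0.01 level, in a sample sized for energy intake. If the morning area inflates the variance of the difference, a real effect on appetite is more likely to be missed.

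**Working it through.** **The plan's own figure.** The only sample-size calculation (section 7.6) concerns daily energy intake: f = 0.175, alpha 0.05, 85% power, within-subject correlation 0.7. With λ = f²·N·m/(1−ρ) and m = 2, N = 46 gives λ = 0.030625 × 46 × 2 / 0.3 = 9.39. On (1, 44) df the power is 0.850, and 46 is the smallest N that reaches 85%, so the stated minimum reproduces. The plan gives no corresponding figure for the AUC test.

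**Share of the window before exposure.** Table 2 allows breakfast at 7:00-10:30, lunch at 12:00-14:00 and dinner at 17:00-19:00 (at least 4 h after lunch), in 30-minute sessions. Share = (lunch start − breakfast start) / (dinner end − breakfast start).

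- Mid-window (8:45, 13:00, 18:00): 4.25 / 9.75 = 43.6%.
- Shortest morning (10:30, 12:00, 19:00): 1.5 / 9.0 = 16.7%.
- Longest morning (7:00, 14:00, 18:00): 7.0 / 11.5 = 60.9%.

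The two extremes let a session start at any time in its window and count the 4 h from the start of lunch. With equally spaced ratings in place of clock time, 2 of 5 trapezoids (40%) precede lunch.

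**Effect on the contrast.** Mid-window ratings fall at 8.75, 9.25, 13, 13.5, 18 and 18.5 h. The trapezoid weights are:

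- full day: 0.25, 2.125, 2.125, 2.5, 2.5, 0.25;
- pre-lunch to post-dinner: 0, 0, 0.25, 2.5, 2.5, 0.25.

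Assume a portion effect δ at each of the last three ratings. Both summaries then have expected difference (2.5 + 2.5 + 0.25)δ = 5.25δ, so the total-AUC contrast is unchanged.

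**Effect on the variance.** Assume also that the between-day difference has the same SD at every rating. With zero correlation the variances are proportional to Σw²: 21.656 for the full day and 12.625 for the restricted window, a ratio of 1.72. The full-day AUC keeps √(1/1.72) = 0.76 of the standardised effect. Power comes from the noncentral t (paired, two-sided 0.01), anchored at 80% on the restricted window. Results are essentially the same at N = 46 and N = 60.

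| Correlation of between-day differences (assumed) | Variance ratio | Power, full-day AUC |
|---|---|---|
| lag-1, 0 | 1.72 | 51% |
| lag-1, 0.3 | 1.99 | 44% |
| lag-1, 0.5 | 2.24 | 38% |
| lag-1, −0.3 | 1.57 | 56% |
| common, 0.3 | 2.44 | 35% |
| common, 0.5 | 2.72 | 31% |
| common, −0.10 | 1.32 | 66% |
| common, −0.15 | 1.07 | 77% |

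**Effect of session times.** With lag-1 correlation 0 to 0.5, if everyone had the shortest morning the full-day power would be about 72-78%; with the longest, about 15-19%.

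**When the loss disappears.** Var(full) = Var(morning) + Var(later) + 2·Cov, so the morning adds variance unless Cov is below −½·Var(morning). This is possible. For the shortest morning and a common correlation of −0.15, variance = 1.15·Σw² − 0.15·(Σw)². The full day gives 1.15 × 25.75 − 0.15 × 81 = 17.46; the restricted window gives 1.15 × 24.625 − 0.15 × 56.25 = 19.88. There the full-day AUC is slightly the better summary.

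**The case against.** The strongest defence is that a whole-day appetite summary is coherent. The primary outcome, daily energy intake, also covers the whole day, including a breakfast whose portions are not manipulated, and a matching daily AUC lets the two be read together. That stands as a reason to keep the full-day AUC in the report. It does not make it the best statistic for section 7.5.2, whose stated question is the effect of portion reduction.

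The second defence is that nothing here is invalid. That also stands. A reader might infer that the morning area biases or dilutes the estimate. For a total AUC it does not: the expected difference is the same in both windows. Only a time-averaged AUC would be diluted, and the plan does not specify one. Breakfast dishware is fully counterbalanced with portion order, so it can add variance but no expected bias.

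Third, a reader might infer that the morning ratings can only add noise. The documents do not support that. All meals are ad libitum, so a hungrier morning could be followed by more eating and less hunger later, and sufficiently negative correlations would remove the loss or reverse it.

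Finally, hunger and fullness do not appear in the objectives table in section 2 and feed neither the primary nor the mediation analysis.

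**Conclusion.** The point holds as a matter of efficiency in a secondary analysis, at low severity. The tested AUC includes a pre-exposure stretch of 44% at mid-window times (about 17% to 61% over permitted times). It has no expected portion effect and will usually cost power.

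The size of the loss is uncertain. At mid-window times, 80% power on the lunch-onwards AUC becomes about 38-51% for lag-1 correlation 0 to 0.5, about 31-35% for a common correlation of 0.3 to 0.5, and about 77% for a common correlation of −0.15. All of these rest on assumed equal SDs, an assumed constant effect from the post-lunch rating and an arbitrary 80% anchor, so none should be quoted as this trial's power. Nor do the documents say that a null result would be reported as showing no effect on hunger; that is a risk of interpretation, not a stated plan.

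**What to change.** In sections 7.2.1 and 7.5.2, define the AUC for the portion-size t-test as running from the pre-lunch to the post-dinner rating on each study day. Report the pre-breakfast-to-pre-lunch AUC separately as a pre-exposure check, where no portion effect is expected. Keep the full-day AUC as a descriptive summary, and state the time axis used.

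The cost is SAP wording and new integration limits; every rating is already collected. There are two downsides. The tested summary would no longer cover the same whole day as daily energy intake, and precision would not improve if morning and later differences proved sufficiently negatively correlated. The change should be fixed before the data are examined.

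### The hunger and fullness AUC is not divided by elapsed time, so differences in length between a participant's two study days add avoidable noise to a secondary test

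*Combined protocol and SAP*

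**What the plan says.** Section 5.2.4 collects hunger and fullness on "visual analog scales ranging from 0 to 100 before and after eating each meal in the lab". Section 7.2.1 says "Each participant will have 12 measures of hunger and fullness", that is, six per study day, and reduces each day to one number by "calculating the area under the curve (AUC) using the trapezoid function". It gives no unit of time, does not choose between recorded and nominal times, and mentions no division by elapsed time. Section 7.5.2 then runs paired t-tests of larger against smaller portions "on AUC for hunger and fullness". Section 7 sets p < 0.01 for secondary analyses.

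Table 2 in section 6 fixes the timing. The first rating belongs to "Breakfast 30 minute session between 7 am and 10:30 am". Lunch falls between 12 pm and 2 pm. Dinner falls between 5 pm and 7 pm, at least four hours after lunch, again as a 30-minute session. On matching the two days, Table 2 asks only that the "two experimental sessions should take place on the same day of the week". Section 6 allows occasional scheduling exceptions, and section 7.3 lets a missed meal be moved to later the same day. Nothing requires the same clock times on both days.

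**The concern.** A trapezoid AUC of ratings over clock time is measured in points times hours. It equals the time-weighted mean rating multiplied by the time from first to last rating, so a longer day gives a larger AUC at the same level of hunger. The pairing removes whatever is stable in a participant's schedule. It does not remove a difference in length between her two days, and the plan permits such a difference.

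The tests in section 7.5.2 are the plan's only check on whether smaller portions leave participants hungrier or less full. They run at a strict threshold with possibly as few as 46 participants. Extra variance makes a non-significant result more likely, and readers may take such a result as reassurance about smaller portions.

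**Working it through.** **Sample size.** The plan states no power for hunger or fullness, so N comes from section 7.6: f = 0.175, within-subject correlation 0.7, two conditions. The noncentrality is f² × N × 2 / (1 − 0.7) = 0.030625 × 46 × 2 / 0.3 = 9.39. This gives 85.0% power at α = 0.05, so the stated 46 reproduces.

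**Span from first to last rating (Table 2).**
- If the windows are start times: shortest 10:30 to 17:30 = 7.0 h; longest 07:00 to 19:30 = 12.5 h.
- If the whole session must fit inside the window: shortest 10:00 to 17:30 = 7.5 h; longest 07:00 to 19:00 = 12.0 h.

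**Scaling.** A constant rating of 50 gives 50 × 7 = 350 on the shortest day and 50 × 12.5 = 625 on the longest, a ratio of 1.79. After division by span, both are 50.

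**What reaches the paired test.** Let T be the typical span, M the mean rating, SD_d the SD of the within-participant difference in mean rating, and SD_T the SD of the within-participant difference in span. To a good approximation:

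variance of the total-AUC difference = (T × SD_d)² + (M × SD_T)²

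inflation relative to the time-divided AUC = 1 + [M × SD_T / (T × SD_d)]²

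The documents give none of these four quantities. Assume T = 10 h, M = 50, SD_d = 8 to 12 points, and a standardised paired effect of 0.5 for the time-divided AUC. Power is from the noncentral t, N = 46, two-sided α = 0.01. With division it is 75%. Without division:

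| SD_T | Inflation, SD_d = 12 | Inflation, SD_d = 8 | Power without division |
|---|---|---|---|
| 0 | 1.00 | 1.00 | 75% |
| 0.5 h | 1 + (25/120)² = 1.04 | 1 + (25/80)² = 1.10 | 71–73% |
| 1 h | 1 + (50/120)² = 1.17 | 1 + (50/80)² = 1.39 | 58–67% |
| 2 h | 1 + (100/120)² = 1.69 | 1 + (100/80)² = 2.56 | 30–47% |

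The loss grows with the mean rating. At SD_T = 1 h, power without division is 66–71% for M = 35 and 48–62% for M = 65.

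**How large could SD_T be?** If breakfast is uniform over 3.5 h and dinner over 2 h, drawn afresh each day, the span variance is about 3.5²/12 + 2²/12 = 1.02 + 0.33 = 1.35. That is an SD of 1.16 h, or 1.16 × √2 ≈ 1.6 h for the difference between two days. The four-hour gap after lunch lowers this only slightly, to 1.59 h.

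**Simulation of the six ratings.** Assumptions: SDs of 12 (person), 8 (day) and 8 (single rating) points; a shift of 8 or 10 points from after lunch onward; plausible hunger and fullness profiles; N = 46; α = 0.01. Power lost by not dividing:

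| Timing across a participant's two days | Power lost (percentage points) |
|---|---|
| Identical | about 1 |
| Span difference SD 0.5 h | 2–4 |
| Span difference SD 1 h | 6–13 |
| Independent across the full windows | 10–24 |

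Type I error stayed near 1% throughout, with and without division.

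**The case against.** Four objections deserve an answer.

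**The plan is silent; it does not reject standardisation.** This stands in part. Section 7.2.1 neither states nor excludes division by time, and the title of its cited method source refers to two formulas without the plan saying which applies. Nominal or equally spaced times would remove the day-length effect. But the plan does not specify those either, and the ordinary reading of a trapezoid AUC of ratings across time is a total over clock time. The silence leaves the time axis to be chosen at analysis.

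**A reader might infer from the 7 to 12.5 h range that day length drives the outcome.** The documents do not support that. The range is the extreme across all participant-days, and the test is paired, so only the difference between one participant's two days matters. The 350-against-625 contrast would enter the test only if the same participant had the shortest possible day once and the longest once.

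**Independent times are close to a worst case.** This stands. Table 2 arranges an individual schedule at screening and puts both days on the same weekday, so some similarity is likely. The 10–24 point loss is therefore an upper-end figure, and with modest variation the loss is a few points.

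**Total AUC and time-weighted mean answer different questions.** True: one is cumulative, the other an average level. Yet the stated purpose in section 7.5.2 is to see whether hunger rises or fullness falls. For that, a level on the rating scale is the more direct measure, and a longer day should not count as more hunger.

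**Conclusion.** The point holds as a minor matter of efficiency. As written, the AUC can carry differences in day length into a paired comparison meant to reflect hunger and fullness, and the schedule rules allow such differences.

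The size depends on how far participants' two days actually differ, which the documents do not let anyone predict. The loss runs from about 1 percentage point of power with identical times to 10–24 with independent times, under the assumed rating SDs and effects.

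It would be wrong to read this as a biased or invalid test. Portion order is randomised, so day length should not differ systematically between conditions, and type I error is not inflated. Daily energy intake, the primary outcome, is unaffected. Nor does the plan commit to concluding that hunger is unchanged: it plans no equivalence test. Division would not make the test strong either. In the simulations, power with division was still only around 37–39% for an 8-point effect and 59–60% for a 10-point effect, so a non-significant result needs cautious wording in any case.

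**What to change.** In section 7.2.1, state that the trapezoid AUC is computed from the recorded time of each rating and divided by the time from first to last rating that day. The result is a time-weighted mean on the 0–100 scale. Make section 7.5.2 refer to this quantity. Reporting the within-participant difference in span between the two days would show readers how much the choice mattered.

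The cost is one sentence in each section, one division per participant-day, and recording of rating times at the in-lab sessions. The result describes an average level, not a cumulative total. Division also leaves the weights on the intervals between ratings dependent on meal spacing, so it removes the effect of total day length but not every effect of timing. In the simulations it did not cost power, even when times matched.
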